# STATEMENT OF COMPLIANCE

This document is a protocol for a clinical research study. The study will be conducted in compliance with all stipulations of this protocol, the conditions of ethics committee approval, the NHMRC National Statement on Ethical Conduct in Human Research (2007) and the Note for Guidance on Good Clinical Practice (CPMP/ICH-135/95).

# PROTOCOL SYNOPSIS

Title	B-cell lymphoma 6 protein (BCL6) as a potential biomarker for endometriosis: can it be used to predict endometriosis' presence and/or severity?						
Objectives	Primary:						
	To evaluate BCL6 expression in luteal phase endometrial biopsy in women						
	with and without endometriosis at laparoscopy.						
	Secondary:						
	1) To assess whether or not there is any correlation between BCL6 levels and						
	the severity of endometriosis at laparoscopy, based on r-ASRM classification						
	2) To assess whether including the results of patients' long-form						
	Endometriosis Health Profile Questionnaire (EHP-30) in the statistical analysis						
	(in combination with their BCL6 result) improves the likelihood of correctly						
	predicting the presence, absence, and/or severity of endometriosis at						
	laparoscopy						
Study Design	Case-control study, based on prospectively-collected data.						
Planned Sample Size	184 participants						
Selection Criteria	Inclusion criteria:						
	- Women aged between 18 – 50yo						
	- Women who have a regular menstrual cycle						
	- Women who are already planning to undertake laparoscopy, for any						
	indication						
	- English speaking						
	Capacity and willingness to give written informed consent						
	- Willingness to comply with the study						
	- Willingness to have their planned procedure undertaken in the						
	luteal phase of their menstrual cycle						

	Exclusion criteria:
	
 
Women who have an absolute contra-indication to endometrial biopsy, such as viable (ongoing) and wanted intra-uterine pregnancy
 
Women with a non-viable or unwanted pregnancy
 
Women who have a relative contra-indication to endometrial biopsy, such as: cervical or uterine infection
 
Women in whom undertaking an (otherwise unnecessary) endometrial biopsy may worsen a pre-existing condition (e.g. Asherman's syndrome, intra-uterine adhesions)
 

Study Procedures	
 
(1) Participants to complete an online questionnaire pre-operatively (long-form EHP-30 questionnaire)
 
(2) Endometrial biopsy to be taken intra-operatively, and sent for analysis of BCL6 levels
 
(3) Endometriosis to be staged intra-operatively using the r-ASRM classification system
 

#### **Statistical Procedures**

## Sample Size Calculation

## **Analysis Plan**

Participants' EHP-30 answers will be uploaded automatically from 'RedCap' to Excel, for analysis using SPSS statistical software. Participants' r-ASRM score will also be entered into Excel. This will be ordinal data; either: no endometriosis, or stage I / II / III / IV endmetriosis. Participants' BCL6 results will be continuous data, ranging from 0 to 4. r-ASRM score versus BCL6 will be presented as a box plot.

Our sample size of 184 patients is based on the following assumptions:

- (1) For approximately one-third of our patients, endometriosis is *not* suspected pre-operatively; 10% of these patients will be found to have endometriosis at laparoscopy
- (2) For approximately two thirds of our patients, endometriosis is expected to be found at laparoscopy; approximately 50% of these patients will be found to have endometriosis at laparoscopy

Therefore, approximately 37% of our patients will have endometriosis. Assuming BCL6 test's sensitivity and specificity for endometriosis are  $\geq$  85% (from Evans-Hoeker et al), a sample size of 184 will provide precision of +/-10% for 95% confidence intervals, and 80% power to detect a difference of 0.374 in average BLC6 levels between controls and cases.

Receiver-operator curve analysis will be performed to assess BCL6 as a biomarker for endometriosis, and to find the optimal cut-off score for BCL6 that differentiates between cases and controls. Students t test will be used to compare mean BLC6 levels between cases and controls. Logistic regression analysis and multi-variable modelling will enable us to ascertain whether or not participants' EHP-30 answers improve the predictive value of BCL6: this results will be presented as a nomogram or classification tree analysis.

P values of <0.05 will be considered significant

# **Duration of the study**

Nine months

# **GLOSSARY OF ABBREVIATIONS**

ABBREVIATION	TERM
AGES	Australasian Gynaecological Endoscopy and Surgery society
ASRM	American Society of Reproductive Medicine
BCL6	B-cell lymphoma 6 protein
CARE	Centre for Advanced Reproductive Endosurgery
EHP-30	Endometriosis Health Profile Questionnaire
HREC	Human Research Ethics Committee
r-ASRM	Revised American Society for Reproductive Medicine
SAE	Serious adverse event
STAT3	Signal Transducer and Activator of Transcription 3
SUSAR	Suspected Unexpected Serious Adverse Reaction

#### 1.5 Funding and resources

Pathology Company 'Douglass Hanly Moir' has agreed to perform the BCL6 tests on endometrial biopsy samples free of charge. In exchange for funding, fertility company 'Genea' will be acknowledged in publications. No study data or personal information will be sent to either of these companies.

## 2 INTRODUCTION AND BACKGROUND

## 2.1 Background Information

Endometriosis is the presence of endometrial glands and stroma in sites other than the uterine cavity. The exact pathogenesis of endometriosis remains controversial, but the most widely held theory is that of 'retrograde menstruation': when endometrial cells flow backwards through the Fallopian tubes and into the peritoneal cavity during menstruation. Hence, endometriotic lesions typically implant on and grow between pelvic organs, such as the ovaries, Fallopian tubes, and the lining of the abdominal and pelvic cavities.

Thought to affect approximately 10% of reproductive-age women, endometriosis can lead to many and varied symptoms, including severe dysmenorrhoea (period pain), dyspareunia (pain during penetrative intercourse), chronic pelvic pain, and infertility.

The diagnosis of endometriosis may be suspected based on a patient's history and physical examination. Imaging modalities (such as ultrasound and magnetic resonance imaging) can strengthen the suspicion of severe endometriosis (e.g. endometriotic ovarian cysts and deeply BCL6 as an endometriosis biomarker Protocol

Page 10 of 47

Version 5, 26/08/2021

infiltrating nodules) with a high degree of sensitivity. However, superficial peritoneal endometriosis cannot be identified by any imaging modality at present.

The only way to definitively confirm the presence or absence of endometriosis is to undertake laparoscopy (keyhole surgery). Undertaking laparoscopy, and excising suspected endometriotic lesions for histological analysis, remains the gold standard for diagnosing and managing endometriosis.

Because there is no reliable non-invasive way to diagnose endometriosis (esp. superficial endometriosis), there is often a significant delay in diagnosis. In addition: in approximately 55% of patients who undertake laparoscopy for pelvic pain (to investigate possible endometriosis), no endometriosis is found.

#### 2.2 Research Question

To what extent are B-cell lymphoma 6 protein (BCL6) levels on endometrial biopsy (taken during the luteal phase) predictive of endometriosis at laparoscopy?

#### 2.3 Rationale for Current Study

As noted above, there is a dire need for a relatively non-invasive diagnostic tool for endometriosis. This would save many women from having an unnecessary laparoscopy: as mentioned above, 55% of women who have laparoscopy to investigate pelvic pain (and a clinical suspicion of endometriosis) do not actually have any endometriosis found at subsequent laparoscopy. In addition, having a reliable non-invasive marker of endometriosis has been predicted to be a paradigm shift for the diagnosis and treatment of infertile women.

In addition, a reliable biomarker would guide the management of some women towards an earlier laparoscopy. For example: *in vitro* fertilisation is half as likely to be successful in women with endometriosis. Diagnosing endometriosis non-invasively and undertaking earlier laparoscopic excision, would improve such women's fecundity, and may negate the need for them to undertake *in vitro* fertilisation at all.

Previous research investigated the possibility of using nerve fibres in endometrial biopsies as a biomarker for endometriosis. There were some promising studies initially; however, these promising results could not replicated by several subsequent research groups.

A promising biomarker that has been explored recently is B-cell lymphoma 6 protein (BCL6): in 2017 Yoo and colleagues concluded that BCL6 is one of several biomarkers that are over-expressed in the endometrium of women with endometriosis, and postulated that it may be involved in endometriosis' pathogenesis. Lessey et al outline how endometriosis leads to sustained activation of a transcription factor called Signal Transducer and Activator of Transcription 3 (STAT3): STAT3 phosphorylation then stimulates BCL6 expression, thereby explaining a possible mechanism for why BCL6 is abnormally high in the endometrium of women with endometriosis. Evans-Hoeker et al undertook a prospective case-control study, and determined that the BCL6 level at which endometriosis was highly likely was 1.4: BCL6 protein expression was significantly higher in the luteal/secretory phase of the menstrual cycle in women with endometriosis, compared to controls

*BCL6 as an endometriosis biomarker* Protocol Version 5, 26/08/2021 Page 12 of 47

(women without endometriosis). A cut-off of 1.4 provides a positive likelihood ratio of 15.4, and a negative likelihood ratio of 0.04 for endometriosis.

Hence, we are proposing to undertake a prospective study, in which patients who are already undergoing laparoscopic surgery (for any indication) have concurrent endometrial biopsy collected, using dilatation and curettage method. The endometrial biopsy sample will be sent for laboratory analysis, to determine the participant's BCL6 level. The patient's endometriosis (or lack thereof) will be surgically staged according to the revised American Society of Reproductive Medicine (r-ASRM) classification system, which is the standard scoring system for endometriosis (please see Appendix 13.1). Statistical analysis will allow conclusions to be made, regarding to what extent BCL6 on endometrial biopsy are predictive of the presence/absence and stage of endometriosis. If so, this will further develop the possible use of BCL6 as a relatively non-invasive biomarker to improve patient counselling and management, potentially negating the need to stage their endometriosis laparoscopically.

#### **3 STUDY OBJECTIVES**

Our null hypothesis is that there is no correlation between BCL6 levels on luteal phase endometrial biopsy between control (no-endometriosis) and women with endometriosis.

## 3.1 Primary Objective

To evaluate BCL6 expression in luteal phase endometrial biopsy in women with and without endometriosis at laparoscopy.

### 3.2 Secondary Objectives

- 1) To assess whether or not there is any correlation between BCL6 levels and the severity of endometriosis at laparoscopy, based on r-ASRM classification
- 2) To assess whether including the results of patients' long-form Endometriosis Health Profile Questionnaire (EHP-30) in the statistical analysis (in combination with their BCL6 result) improves the likelihood of correctly predicting the presence, absence, and/or severity of endometriosis at laparoscopy

# 4 STUDY DESIGN

This study will be designed and carried out in compliance with the National Health and Medical Research Council's 'National Statement on Ethical Conduct in Human Research'.

*BCL6 as an endometriosis biomarker* Protocol Version 5, 26/08/2021 Page 13 of 47

#### 4.1 Type of Study

Case-control study, derived from prospectively-collected samples.

### 4.2 Study Design

This will be a case-control study, derived from prospectively-collected samples.

Women who fulfil the selection criteria will be invited to participate in the study. Many of these women will already be planned to undertake a concurrent endometrial biopsy, at the time of their laparoscopy. If not: we will talk them through a consent form for endometrial biopsy, using the standard dilatation and curettage method. If they agree to participate, their procedure will be booked to occur during the luteal phase of their menstrual cycle (i.e. the two weeks leading up to an expected period).

A urinary pregnancy test will be completed immediately pre-operatively (i.e. on the day of the planned operation), to exclude any pregnant women (as per the exclusion criteria outlined below).

Patients will be asked to complete an online version of the long-form EHP-30 questionnaire preoperatively. The EHP-30 is a reliable, validated instrument to measure the health-related quality of life of women with endometriosis. It asks participants (over the course of 30 questions) to recall how often in the last four weeks they have experienced various symptoms of endometriosis. The 'longform' version includes six additional sections (using 23 questions) covering areas such as: work; relationships with children; sexual relationship(s); and feelings about the medical profession, treatment, and infertility.

At their planned procedure, endometrial biopsy will be taken, using the standard dilatation and curettage method. As a guide, approximately 0.5cm3 of tissue will be biopsied, weighing approximately 2 grams. The endometrial biopsy sample will be sent to the laboratory for analysis of the BCL6 level. Laparoscopy will be undertaken (as planned), and the patient's endometriosis (if present) will be scored. Clinicians will use the best-known, and most widely used, classification system for endometriosis: the revised American Society for Reproductive Medicine (r-ASRM) classification system (please see Appendix 13.1). This involves documenting and scoring patients' endometriotic implants (seen at laparoscopy) based on their location and size, the location and thickness of any adhesions (internal scarring), plus the extent to which the 'Pouch of Douglas' (the area between the uterus and bowel) is involved. Patients will then end up being classified as having either: no endometriosis; stage I (minimal); stage II (mild); stage III (moderate); or stage IV (severe) endometriosis.

*BCL6 as an endometriosis biomarker* Protocol Version 5, 26/08/2021 Page 14 of 47

Later statistical analysis will aim to determine to what extent patients' BCL6 levels (on luteal phase endometrial biopsy) is predictive of the presence and severity of endometriosis at laparoscopy. Additional analysis will include patients' EHP-30 results as a predictive variable, to assess if the combination of BCL6 level plus EHP-30 answers improves the predictive value of these two screening tools for endometriosis.

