#### 10.3 Statistical Analysis Plan

Regarding participants' answers to questions in the EHP-30 questionnaire: RedCap automatically exports data to statistical software SPSS, which will be used to perform the statistical analysis. Participants' BCL6 levels will be uploaded into the relevant section of the SPSS document used for this research, as will participants' endometriosis severity (based on the r-ASRM classification system).

Participants' BCL6 results will be continuous data, with their BCL6 HSCORE ranging from 0 to 4. Participants' endometriosis severity will be ordinal data, in that all participants will be categorised into one of five distinct groups: no endometriosis; stage I (minimal) endometriosis; stage II (mild) endometriosis; stage III (moderate) endometriosis; or stage IV (severe) endometriosis. It is expected that participants' BCL6 results by endometriosis severity will be presented in a boxplot.

Receiver-operator characteristic analysis will be performed to assess the usefulness of the biomarker and to find the optimal cut-off score for BLC6 that differentiates best between cases and controls.

Students t test will be used to compare mean BLC6 levels between cases and controls.

Regarding participants' EHP-30 questionnaire results: logistic regression analysis and a multi-variable model will enable us to ascertain whether including particular aspects of the long-form EHP-30 improves the predictive value of BCL6 in finding endometriosis at laparoscopy. If any such relationships are found, it is expected that these results could be presented as a nomogram, or classification tree analysis.

The statistical comparisons will be performed using statistical software SPSS (IBM), with P values < 0.05 considered significant.

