15.1 Revised **ASRM** classificatio n system for endometri osis

# 15.5 Case report form (CRF)

# **Case report form**

				Participant ID number: I I	_1_1_1
Inclusion criteria (see below):	M	let		Not met	
- Age between 18 – 50yo	)				
- Regular menstrual cycle	e (i.e. mens	trual	cycle le	ngth 21 - 35 days inclusive)	
- Already planning to un	dertake lap	arosc	copy, for	any indication	
- English speaking					

 
Capacity and willingnes
 
	s to give w	ritten	inform	ed consent	
- Willingness to comply v	with the stu	ıdy			
- Willingness to have the	neir planne	ed pr	ocedure	e undertaken in the luteal pha	ise of their
menstrual cycle (see be	elow)				
Date of last menstrual period:	/	/	/	_	
Date of next expected menstru	ual period:		_/	_/	
Date of informed consent:	/	/		Date of procedure:/	/
Is the date of next expected me	enstrual pei	riod ii	n the tw	o weeks following the planned p	orocedure?
	Ye	es		No	
NB: If 'no': this patient is not in	n the luteal	phas	se of he	r menstrual cycle, so is ineligible	for inclusion
in this study.					
Primary surgeon:	A/[name]	m		A/[name]	
	[name]				
EHP-30 questionnaire complet	ed				
Urine pregnancy test complete	ed, and neg	ative	result r	eported	
BCL6 sample sent to DHM labo	ratory				

*BCL6 as an endometriosis biomarker* Protocol Version 5, 26/08/2021 Page 45 of 47

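### The CRF dates place each biopsy within the two-week luteal window, but section 10.3 compares BCL6 without them, so any trend or timing difference goes unadjusted

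*Protocol*

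**What the plan says.** - Section 4.2 has each participant's operation booked in the luteal phase, "i.e. the two weeks leading up to an expected period". Section 6.2 makes willingness to be operated on in that phase an inclusion criterion and admits cycles of 21 to 35 days.
- The case report form (15.5) has fields for "Date of last menstrual period", for the next expected period and for "Date of procedure". It states one use for them. If the expected period does not fall within two weeks after the procedure, the patient is not in the luteal phase of her "menstrual cycle, so is ineligible".
- Section 10.3 (and section 10 in the same words) fixes the comparison: "Students t test will be used to compare mean BLC6 levels between cases and controls". ROC analysis is to be done "to find the optimal cut-off score for BLC6 that differentiates best between cases and controls". The only added predictors named for the logistic and multivariable models are parts of the EHP-30.
- Section 2.3 gives the background for luteal sampling: "BCL6 protein expression was significantly higher in the luteal/secretory phase of the menstrual cycle in women with endometriosis", compared with controls.
- No section adjusts, stratifies or runs a sensitivity analysis by cycle day.

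**The concern.** The protocol treats the phase of the cycle as important enough to restrict sampling to it, and the window it then allows is 14 days wide. The data needed to locate each biopsy in that window are already collected, yet they serve only as a yes/no gate.

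Two things are at stake. If BCL6 changes with day inside the window, that variation adds to the error in the comparison of means. If cases and controls are also operated on at different average days, the same variation becomes bias in the mean difference, and it can shift the pooled cut-off too.

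Timing is not randomised, and the two groups come from different mixes of indications, surgeons and hospitals (sections 4.4, 6.1 and 10.1). A difference in timing is therefore possible, although none is described. The point concerns variation among women who are in the luteal phase, not whether the gate identifies that phase correctly.

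**Working it through.** **Inputs from the protocol.** 68 cases and 116 controls, difference 0.374, 80% power, two-sided 5% (section 10.1); 14-day window (section 4.2). The protocol states no SD and no trend of BCL6 by day.

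**1. The plan's own figure.** Without an SD the 80% cannot be reproduced forwards, so it is solved backwards.
- sqrt(1/68 + 1/116) = 0.1527.
- Normal approximation: SD = 0.374 / (0.1527 × (1.960 + 0.842)) = 0.874. With the noncentral t the SD is 0.869.
- The standardised difference is 0.374 / 0.869 = 0.43. Nothing here contradicts the stated power.

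**2. Precision, timing balanced between groups.** Assume a linear change of Δ HSCORE units across the 14 days and biopsy days spread evenly. The share of within-group variance explained by day is R² = (Δ²/12) / 0.869². The adjusted comparison has residual SD 0.869 × sqrt(1 − R²). Power comes from the noncentral t.

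| Assumed Δ over 14 days | R² | Power after adjustment |
|---|---|---|
| 0 | 0 | 80% |
| 0.5 | 0.0208 / 0.755 = 3% | 81% |
| 1.0 | 0.0833 / 0.755 = 11% | 84% |
| 1.5 | 0.1875 / 0.755 = 25% | 90% |

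The last row assumes a trend four times the planned difference (1.5 / 0.374 = 4.0) and is an extreme. All rows assume that day is known without error, so the gains are upper limits.

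**3. Bias, if timing also differs.** Bias = Δ × (gap in mean day) / 14. For an assumed 2-day gap:
- Δ = 0: 0
- Δ = 0.5: 0.071, or 19% of 0.374
- Δ = 1.0: 0.143, or 38%
- Δ = 1.5: 0.214, or 57%

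At R² = 0.10 with a 2-day gap, the type I error of the unadjusted test is about 18%. In simulation, adjusting for day returned it to about 5%.

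**4. How plausible is a 2-day gap?**
- With even, random booking the SD of day is 14 / sqrt(12) = 4.04. The difference in mean day then has SD 4.04 × 0.1527 = 0.62 day. A 2-day gap is 2 / 0.62 = 3.2 SDs, so it would need a systematic cause.
- Section 10.1 shows one possible route. Cases from the suspected-endometriosis stream: (2/3 × 0.50) / 0.367 = 91%. Controls from that stream: (2/3 × 0.50) / 0.633 = 53%. If the two streams were booked 2 days apart on average, cases and controls would differ by 2 × (0.91 − 0.53) = 0.77 day. The bias would be 7%, 15% or 22% of 0.374 for Δ = 0.5, 1.0 or 1.5.

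**5. What adjustment costs.** One degree of freedom. With a 2-day gap the variance of the adjusted difference is inflated by 1 + (2 / (4.03 × 0.1527))² / 182 = 1.058, where 4.03 is the SD of whole days 1 to 14. At R² = 0.05 the adjusted standard error is then about equal to the unadjusted one (ratio 1.003). In that setting the gain is removal of bias, not precision.

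**The case against.** The strongest case against acting is that the premise is unproven. The finding cited in section 2.3 contrasts women with and without endometriosis in the luteal phase; it does not say that BCL6 changes from day to day within that phase. Restricting sampling to one phase already controls for phase, and sections 2.3 and 2.4's preceding rationale rely on a single luteal cut-off of 1.4. No section describes different booking for cases and controls, and section 4.2 applies one rule to all. An unadjusted t test and a pooled ROC analysis are standard for the research question in section 2.2, and a covariate analysis could sit in a separate plan not seen here.

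Most of this stands. A reader might infer that the plan demonstrably wastes precision, or that it leaves a known scheduling imbalance uncorrected. The documents support neither: zero trend and balanced timing are both compatible with them, and under either condition there is no bias. A reader might also take the form to give the true time to the next period. It gives a forecast, in women whose cycles may run from 21 to 35 days.

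It might also seem natural to report cut-off performance for each luteal week. With about 34 cases a week, the half-width at 85% sensitivity is 1.96 × sqrt(0.85 × 0.15 / 34) = 12 points, outside the ±10% that section 10.1 plans for.

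What does not stand is that nothing need be said. Section 10.3 carries the title of the statistical analysis plan and names its tests, and the recorded dates are absent from all of them.

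**Conclusion.** The point holds as a low-cost improvement, not as an error. The dates are collected, their only stated use is the eligibility gate, and the planned comparison leaves any trend in the error term and any timing difference uncorrected.

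The size depends wholly on assumptions the documents do not supply. The power gain is nil with no trend and about 1 to 4 points if day explains 3% to 11% of the variance. Bias needs both a trend and a gap in mean day. It is 19% to 38% of 0.374 for those same trends with a 2-day gap, and 7% to 15% if the 2-day gap lies only between the indication streams. The sample size of 184, the 68/116 split, the 80% power and the 0.374 are all unaffected.

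**What to change.** In section 10.3:

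1. Derive days from procedure to next expected period from the CRF dates, and report its distribution for cases and for controls.
2. Alongside the t test, prespecify a linear model comparing mean BCL6 between cases and controls with this variable as a covariate.
3. Keep the pooled ROC analysis and single cut-off as the main accuracy analysis, since they answer the question in section 2.2. Any day-adjusted ROC or logistic model should be a sensitivity analysis only, because it changes the target to day-specific accuracy. Do not add cut-off results by luteal week.
4. State that the expected date is a forecast, so adjustment corrects only in part.

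The cost is a few sentences of analysis wording and one degree of freedom among 184 women. No new data, procedures or participants are needed. Fixing the model before the data are seen also avoids a later data-driven choice of whether to adjust.

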#### **5 STUDY TREATMENTS**

Some participants in this study would already be planning to undertake endometrial biopsy, in addition to planned laparoscopy (for example, to investigate heavy menstrual bleeding). Others may originally only be planning to undertake laparoscopy, and will (if they participate) undergo an endometrial biopsy (as part of this study), over and above the planned laparoscopy.

While the patient is anaesthetised, endometrial biopsy will be performed using a 'dilatation and curettage' technique. This involves:

- Gently dilating the cervical canal up to 5mm diameter, using 'cervical dilators'
- Using a 'curette' to take a sample of the lining of the uterus ('endometrium')

This procedure is outlined in the attached 'Patient information and consent' form, as are the potential complications, including:

- Uterine perforation (approximately 1 in 300 women)
- Formation of intra-uterine adhesions (scar tissue) (approximately 1 in 60 women)
- Cervical injury (approximately 1 in 25 women)
- Infection (approximately 1 in 20 women)
- Blood loss > 100mLs (approximately 1 in 10 women)

(Please see Appendix 13.2 for this document.)

The potential implications of the above possible complications and their management include:

(1) Uterine perforation: collection of blood tests for full blood count; injury to bladder or bowel

(1 in 15 patients who have a uterine perforation); intra-abdominal haemorrhage (1 in 6
patients who have a uterine perforation); need for laparotomy (very rare)

*BCL6 as an endometriosis biomarker* Protocol Version 5, 26/08/2021 Page 16 of 47

- (2) Intra-uterine adhesions: lighter menstruation (4 in 5 women with intra-uterine adhesions); sub-fertility (1 in 8 women with intra-uterine adhesions); cyclic pelvic pain (1 in 30 women with intra-uterine adhesions); recurrent pregnancy loss (1 in 8 women with intra-uterine adhesions). Management of the above issues involves hysteroscopy (a procedure performed under general anaesthetic to visualise the lining of the uterus with a small video camera), and resection of the intra-uterine adhesions (separating the intra-uterine scarring, using 'diathermy' electrosurgical devices).
- (3) Cervical injury: repair of any cervical tear is performed immediately, using several absorbable stitches.

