#### **6 PARTICIPANT ENROLLMENT AND RANDOMISATION**

#### 6.1 Recruitment

Patients are referred to our gynaecology clinics by other clinicians (e.g. general practitioners, other gynaecologists, fertility specialists) for a range of gynaecological complaints and conditions, including: pelvic pain, pelvic organ prolapse, leiomyomata, endometriosis, ovarian cysts, infertility, heavy menstrual bleeding, and urinary incontinence. All patients who fulfil the inclusion criteria (as outlined below) will be invited to participate.

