#### 6.2 Eligibility Criteria

Inclusion criteria will be:

- Women aged between 18 50yo
- Women who have a regular menstrual cycle (i.e. menstrual cycle length 21 35 days inclusive)
- Women who are already planning to undertake laparoscopy, for any indication
- English speaking
- Capacity and willingness to give written informed consent
- Willingness to comply with the study
- Willingness to have their planned procedure undertaken in the luteal phase of their menstrual cycle

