## Exclusion criteria will include:

- Women aged < 18yo or > 50yo
- Women with an irregular menstrual cycle (i.e. menstrual cycle length < 21 days or > 35 days)
- Women who have an absolute contra-indication to endometrial biopsy, such as viable (ongoing) intra-uterine pregnancy
- Women who have a relative contra-indication to endometrial biopsy, such as: active cervical or uterine infection
- Women in whom undertaking an (otherwise unnecessary) endometrial biopsy may worsen a pre-existing condition (e.g. Asherman's syndrome, intra-uterine adhesions)

Women with an unwanted / non-viable pregnancy will also be excluded, as the potential risks of undertaking a dilatation and curettage in that context are significantly higher than in a non-gravid (not pregnant) uterus. A urinary pregnancy test will be completed immediately pre-operatively (i.e. on the day of the planned operation, in the pre-operative / admission area of the relevant hospital), to exclude any pregnant women.

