# 6.6 Participant Withdrawal

Participants are able to withdraw from the endometrial biopsy part of the study up until they are anaesthetised. Should any participants ask to withdraw from the study pre-operatively, endometrial biopsy will not be undertaken.

Should they later decide that they want to withdraw from the study, their data can be removed from the database up until the point of analysis.

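### All procedures fall in the two weeks before the expected period, so one same-day urine test cannot be relied on to detect a current-cycle conception, and no visible eligibility criterion or CRF item covers that gap

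*Protocol*

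**What the plan says.** **Timing.** Section 4.2 has each procedure "booked to occur during the luteal phase of their menstrual cycle (i.e. the two weeks leading up to an expected period". Section 6.2 makes agreement to this an inclusion criterion: "Willingness to have their planned procedure undertaken in the luteal phase of their menstrual cycle". The CRF (section 15.5) records the last and the next expected period, and declares a woman ineligible if the next one is not due within two weeks after the procedure.

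**Pregnancy check.** Section 4.2 states: "A urinary pregnancy test will be completed immediately pre-operatively (i.e. on the day of the planned operation), to exclude any pregnant women". The exclusion part of section 6.2 repeats the same test, done "in the pre-operative / admission area of the relevant hospital), to exclude any pregnant women". The CRF has one box for a completed, negative test.

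**Who is exposed.** Section 5 notes that some women would have had a biopsy anyway, and then: "Others may originally only be planning to undertake laparoscopy, and will (if they participate) undergo an endometrial biopsy (as part of this study". The referral reasons in section 6.1 include "leiomyomata, endometriosis, ovarian cysts, infertility, heavy menstrual bleeding, and urinary incontinence".

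**Leaving out the biopsy.** Section 6.6 says: "Should any participants ask to withdraw from the study pre-operatively, endometrial biopsy will not be undertaken".

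**The concern.** The protocol takes pregnancy seriously. Section 6.2 treats a viable intra-uterine pregnancy as an absolute contra-indication to biopsy. It also excludes unwanted or non-viable pregnancy, because curettage then carries more risk. Yet the study requires surgery in the part of the cycle when a urine test says least about a conception in that same cycle, and then rests on that test.

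A woman who conceived a few days earlier could satisfy every written check, test negative, and undergo curettage. Where the biopsy was added only by the study, she has no clinical benefit to set against the risk. The pool includes women referred for infertility, some of whom may be trying to conceive. What is at stake is the possible loss of a wanted early pregnancy, not the validity of the BCL6 comparison.

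**Working it through.** The protocol gives no figure on this point, so there is none to reproduce. The check is a reading of the text and an illustrative count of dates.

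**Text, side by side**
- Sections 4.2 and 6.2 and the CRF all place the procedure before the expected period.
- Sections 4.2 and 6.2 and the CRF name the same single urine test.
- The lists in section 6.2 do not mention contraception, abstinence, intercourse in the study cycle, or a second test.
- The CRF uses the last period date only to confirm the luteal phase.
- The schedule in section 7 has the criteria discussed again on the day of the procedure, but no visible criterion covers this point.

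**Inputs for the count**
- From the protocol: procedure *d* = 1 to 14 days before the expected period, giving 14 permitted dates.
- Assumed, because the protocol gives none of these: luteal length *L* = 12 to 16 days; urine test first positive on day *D* = 8 to 14 after ovulation; implantation on day *I* = 6 to 10.
- Day after ovulation on which the test is done: *p* = *L* − *d*.

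**Dates after ovulation when the test is uninformative about a same-cycle conception** (0 ≤ *p* < *D*)

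| *L* | range of *p* | *D* = 8 | *D* = 14 |
|---|---|---|---|
| 12 | −2 to 11 | 8/14 | 12/14 |
| 14 | 0 to 13 | 8/14 | 14/14 |
| 16 | 2 to 15 | 6/14 | 12/14 |

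The range is 6/14 = 43% to 14/14 = 100%. It includes days before implantation.

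**Dates when a pregnancy has implanted but the test is still negative** (*I* ≤ *p* < *D*), over the 32 pairs with *D* ≥ *I*
- Minimum 0/14, only where *D* = *I* (pairs 8–8, 9–9 and 10–10).
- Maximum 8/14 = 57%, at *I* = 6, *D* = 14 and *L* of 14 or more (*p* = 6 to 13).
- *I* = 9 and *D* = 12 gives *p* = 9, 10, 11, which is 3/14 = 21% for every *L* from 12 to 16.

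The size of the gap depends on the assumed days. That there is a gap needs only that the test does not turn positive immediately after conception.

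**The case against.** The strongest reply is that the patient information and consent forms are not in the text available for review. Advice about intercourse or contraception in the study cycle would naturally sit there, and section 6.3 gives women the form at least two weeks before surgery. This stands as a limit: a reader might infer that participants receive no such advice, and the documents do not support that. Advice in a consent form would still not be an eligibility condition or a recorded check.

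Second, the exclusion list is worded as non-exhaustive, and the criteria are discussed again on the day. A surgeon told of a possible conception could exclude the woman. That is true, but nothing visible prompts the question.

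Third, a reader might take the test's stated purpose as a false claim or a contradiction. It is neither. The sentence says what the test is for, and the test does detect pregnancies from earlier cycles; late in the window it may also detect some from the current one. The safeguard is incomplete, not wrong.

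Fourth, a reader might want a number of women affected. With the share at risk (*f*), the conception probability per cycle (*c*) and the detection day (*D*) all assumed, the expected number is 184 × *f* × *c* × *D*/14. It runs from 184 × 0.10 × 0.02 × 8/14 = 0.2 to 184 × 0.50 × 0.15 × 14/14 = 13.8. A spread that wide, set wholly by assumption, is not an estimate.

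**Conclusion.** The point holds as a gap in the visible eligibility text and CRF. The protocol fixes surgery before the expected period and relies on one same-day urine test, which cannot be relied on for a current-cycle conception. Under the stated assumptions the test is uninformative on 43% to 100% of permitted dates, and negative despite implantation on 0% to 57%. These are shares of dates, not of women. How often it would happen cannot be derived from the documents.

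The conclusion rests on one outside premise, that urinary hCG is not detectable at once after conception, and on the consent forms being unseen. It is a participant-safety point of minor to moderate severity, held with medium confidence. Nothing here bears on power or sample size, and no effect on the BCL6 results is claimed.

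**What to change.** - **Criterion and CRF item.** In section 6.2, and on the CRF beside the last period date, add an item for all participants that pregnancy in the current cycle is reasonably excluded: no unprotected intercourse since the last period, through abstinence, consistent barrier use, sterilisation, or an effective method already in use. Keep the negative urine test alongside it.
- **Hormonal contraception.** State that it is not to be started for the study, since it could disturb the sample that the primary objective needs: "To evaluate BCL6 expression in luteal phase endometrial biopsy in women with and without endometriosis at laparoscopy".
- **If the item is not met.** For a study-only biopsy, the investigator omits it, with the planned laparoscopy going ahead on clinical grounds, or rebooks in a later cycle. This needs a new sentence, because section 6.6 covers only withdrawal at the participant's request. Where the biopsy was already clinically planned, discuss the risk and offer rebooking.
- **Wording.** Say in sections 4.2 and 6.2 that the urine test may miss a current-cycle conception.
- **Consent.** Give the advice with the information form at least two weeks before surgery (section 6.3), and check that both consent forms agree.
- **Counting.** Record how many women are deferred or excluded for this reason.

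The cost is an eligibility line, a CRF box, a few sentences and a consistency check, with no extra visit. The downside is that some women trying to conceive must avoid conception for one cycle, be deferred, or not take part. Section 2.3 names infertile women among those the marker is meant to help, so the case mix may shift slightly. For each woman deferred, one cycle of 21 to 35 days is 21/182 = 12% to 35/182 = 19% of the six-month recruitment and surgery period in section 4.5. The clinical wording is for the investigators and the ethics committee.
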